Evaluate the AUC with alternative Exposure Variable (intercept/ slope): We will compare discriminative ability of our primary model to a model with two exposure variables (intercept (mean mobilization dose for each patient) and slope) utilizing Net Reclassification Index, Brier Score and c-statistics.

Generalized propensity score: In an exploratory approach, accounting for the degrees of freedom available, we will include a generalized propensity score to reduce bias induced by discrepancies in patient characteristics. The propensity score will be generated from different covariates identified as influencing the exposure including APACHE, GCS at enrollment, ASA at admission, PSS-Morbidity, duration of ventilation, duration of sedation, duration of delirium, opioid dose, vasopressors. The propensity score will be confined for a binary exposure variable. To derive at a binary variable, we will categorize the mean mobilization dose (MQS) into two categories, high vs. low.

Subgroup analyses: We will perform a subgroup analysis in patients who received surgery upon admission to the ICU.

Planned Exploratory Analyses

We aim to explore the association of other variables that can be used to quantify mobilization intensity and duration (other than the composite exposure MQS) and adverse discharge disposition.

The additional variables used to quantify mobilization intensity and/or dose are:

- Mean highest achieved level of mobilization therapy (Daily highest achieved ICU mobilization scale level/ICU days)
- Highest achieved mobilization level using ICU mobilization score
- Mean number of daily mobilization sessions (Total number of mobilization units/ICU days)
- Mean duration of mobilization units according to MQS (Total duration of mobilization treatment based on MQS/number of sessions throughout the ICU stay)
- Fraction of days mobilized (Number of mobilization days/ ICU days)
- Early mobilization frequency (Total number of mobilization units from day 1 through 3 on the ICU)

We will use multivariable logistic regression for exploratory analyses analyzing the association between the above-mentioned variables used to quantify mobilization intensity and/or dose.

3. Secondary Aim

Exposure variable

The RFCSA assessed through bedside ultrasound measurements within 48h is used as a continuous exposure variable.

Outcomes

The outcome for the secondary aim of the study is the repeatedly measured daily mobilization dose as quantified by the MQS.

Hypothesis

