Primary hypothesis

The primary hypothesis is that RFCSA is an independent predictor of mobilization dose in the SICU.

Statistical Analysis

All analyses are performed prospectively with prespecified endpoints and statistical methods.

We will conduct a generalized linear mixed effect model to analyze whether the RFCSA quantified via bedside ultrasound is an independent predictor of daily mobilization dose in the ICU.

Predefined confounders include the Barthel Index at hospital admission, APACHE2 and Charlson Comorbidity Index (CCI).

Secondary analysis

We will conduct a generalized linear mixed effect model to analyze whether the RFCSA quantified via bedside ultrasound is an independent predictor of daily mobilization dose in the ICU utilizing an alternative exposure variable. The exposure variable will be the binary variable "Sarcopenia

yes/no". Sarcopenia is quantified by RFCSA assessed through bedside ultrasound measurements within 48h. We will apply Youden's Index to define the optimal cutoff point of RFCSA for Sarcopenia. (Mueller, Eikermann 2016).

Sarcopenia is a clinical syndrome that describes progressive and generalized loss of skeletal muscle mass and strength and is associated with patient outcomes. (Delmonico, Harris, Lee, J Am Geriatr Soc, 2007)

Sample Size and Power

Based on data obtained by the same centers in the SOMS trial (Schaller et al., 2016) there is a correlation between mobilization dose and discharge disposition of 0.25. We therefore calculate that a sample size of 150 patients provides a power of >0.8 to identify a significant effect (alpha-error: 0.05) for our primary outcome.

Data collection

Data collection

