On ICU admission, patients' baseline characteristics [age, sex, race, ethnicity, height, weight, admission diagnoses, Charlson comorbidity index (CCI), ASA PS, Frailty Score, Short Nutritional Assessment Score Questionnaire (SNAQ) Score reason for ICU admission] will be noted. Admission laboratory data and vital signs to calculate the APACHE II score, will be recorded as well as the severity of organ dysfunction [Sequential Organ Failure Assessment (SOFA) score]. SOFA scores will be obtained within 48 hours of SICU admission and on days when follow up ultrasound measurements are conducted (every 8 days/ at ICU discharge). Daily laboratory data, vital signs, medication and ventilation/ABG will be noted. We will further collect data at ICU discharge, Hospital discharge and 3 months after discharge. A summary of the data that we will collect is listed below.

Baseline

Medical Record Number, First name, Last name , Date of Birth, Age, Sex, Race, Ethnicity, Height, Weight at ICU admission, ICU admission [date] , Hospital admission [date], Admission category, Patient had surgery prior to inclusion (y/n) Date of surgery, Surgery CPT Code, Charlson Comorbidity Index, ASA, Frailty Phenotype Modified, Short Nutritional Assessment Questionnaire, APACHE II, Barthel Index 2 weeks prior to admission, Glasgow Coma Scale motor component at enrollment, Absence of lower extremity (y/n), Pregnancy (y/n), Procedural Severity Score.

Follow-up

Richmond Agitation and Sedation Score (RASS), SOFA score, Medical Research Council Muscle scale (MRC scale), Confusion Assessment Method for the ICU (CAM-ICU), Nutrition, Renal replacement therapy (y/n)

Mobility

MQS score, SOMS score, Physical Therapy (PT) time [mins], nonPTMobilization [mins], walking distance [feet], Rectus femoris diameter left [cm²], Rectus femoris diameter right [cm²]

Vital Signs

Systolic blood pressure, diastolic blood pressure, mean arterial blood pressure (MAP), Respiratory rate, Body temperature, Heart rate.

Laboratory

Hb [g/dL], Hk, Creatinine [mg/dL], Urine output [μ mol/L], Alb (g/dL), INR, blood Glucose [mg/dL], serum sodium (Na) [mEq], K [mEq/L], glomerular filtration rate (GFR), Bilirubin [μ mol/L], CRP, WBC count, CKD, Platelets [$\times 10^9/L$].

Medication

Sedation needed (y/n), Steroids (y/n), Opioids total dose per day [morphine equivalent dose, mg], Vasopressors (y/n), NMBAs (y/n + drug), Propofol (y/n), Total propofol dose per day.

Ventilation/ABG

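### The secondary-aim models leave out age, which is collected, so an RFCSA effect on mobilization dose could contain residual age confounding of unknown size

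*SAP*

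**What the plan says.** SAP section 3 (Secondary Aim) states the hypothesis as: "The primary hypothesis is that RFCSA is an independent predictor of mobilization dose in the SICU". The exposure is set by "The RFCSA assessed through bedside ultrasound measurements within 48h is used as a continuous exposure variable" and the outcome by "The outcome for the secondary aim of the study is the repeatedly measured daily mobilization dose as quantified by the MQS". A generalized linear mixed effect model is planned, with this adjustment set: "Predefined confounders include the Barthel Index at hospital admission, APACHE2 and Charlson Comorbidity Index (CCI"). The secondary analysis replaces continuous RFCSA with a sarcopenia yes/no variable and names no covariates of its own.

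Age is available. The Data collection section opens its list with "baseline characteristics [age, sex, race, ethnicity, height, weight, admission diagnoses", and the Baseline list repeats it: "Date of Birth, Age, Sex, Race, Ethnicity, Height, Weight at ICU admission". The SAP gives no reason for leaving age out of the secondary-aim models. Its planned sensitivity analyses stand under the primary aim. Under Covariate Data in section 2, RFCSA is corrected for sex against reference values in healthy adults, but no age correction of RFCSA is described anywhere.

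**The concern.** The answer to the secondary aim is a claim of independence, and such a claim is only as good as its adjustment set. The three listed scores cover prior function, acute severity and comorbidity. Age precedes both muscle area and mobilization, so adjusting for it removes no part of an RFCSA effect. It could plausibly lower both. If it does, and the three scores do not fully carry its influence on mobilization, patients with small RFCSA will be mobilized less partly because they are older. The models would then credit that part to muscle area. The bias would favour the hypothesis under test, in the continuous RFCSA model and in the sarcopenia model alike.

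**Working it through.** **The plan's own figure.** The only power statement, under Sample Size and Power, concerns the primary outcome: "there is a correlation between mobilization dose and discharge disposition of 0.25", with 150 patients and power above 0.8. By Fisher z, atanh(0.25) × √147 = 0.2554 × 12.12 = 3.097, and Φ(3.097 − 1.96) = 0.872 two-sided. The figure reproduces. It neither supports nor refutes the point here. The SAP gives no calculation for the secondary aim.

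**Inputs.** From the SAP: 150 patients, 5% alpha (taken as two-sided), and the three covariates. Everything else is assumed, in standardized units:
- no true RFCSA effect on MQS;
- effects on MQS of −0.25 (APACHE2), 0.20 (Barthel) and −0.10 (CCI);
- RFCSA and the covariates related to each other only through age;
- age–RFCSA correlation −a, with a from 0.3 to 0.5;
- direct age effect d on MQS, from 0 to −0.25 SD per SD;
- base correlations of age with APACHE2, Barthel and CCI of 0.35, −0.30 and 0.30.

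**Formulas.** Let V be the share of age variance that the three covariates leave unexplained:

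V = 1 / (1 + Σ c²/(1 − c²)), where c is each covariate's correlation with age.

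Base case: V = 1 / (1 + 0.1396 + 0.0989 + 0.0989) = 0.748.

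The spurious partial correlation of RFCSA and MQS given the three covariates is

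r = a|d|V / √[(1 − a²(1 − V)) × (1 − v + d²V)],

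where v is the MQS variance explained by age and the covariates together. In the base case v = d² + 2(0.1775)|d| + 0.1319. Here 0.1775 = 0.25×0.35 + 0.20×0.30 + 0.10×0.30, and 0.1319 is the part due to the covariates alone.

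The rejection rate uses m = atanh(r) × √(150 − 3 − 3) = 12 atanh(r), and equals Φ(m − 1.96) + Φ(−m − 1.96).

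**Worked extreme, a = 0.5 and d = −0.25.** v = 0.0625 + 0.0888 + 0.1319 = 0.283. The numerator is 0.5 × 0.25 × 0.748 = 0.0935. The denominator is √(0.937 × 0.764) = 0.846. So r = 0.111, m = 1.33, and the error is Φ(−0.63) + Φ(−3.29) = 0.265.

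**Range over a = 0.3 to 0.5:**

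| Age correlation with APACHE2, Barthel, CCI | Direct age effect d | Spurious r | Error at nominal 5% |
|---|---|---|---|
| 0.35, −0.30, 0.30 | 0 | 0 | 5% |
| same | −0.05 | 0.01–0.02 | 5–6% |
| same | −0.10 | 0.025–0.04 | 6–8% |
| same | −0.15 | 0.04–0.06 | 7–12% |
| same | −0.25 | 0.06–0.11 | 12–27% |
| 0.50, −0.40, 0.60 | −0.15 to −0.25 | 0.03–0.08 | 6–16% |
| 0.50, −0.40, 0.70 | −0.15 to −0.25 | 0.02–0.07 | 6–13% |

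In the last row V falls to 1 / (1 + 0.333 + 0.190 + 0.961) = 0.40, so the scores remove more of the age effect but not all of it. With age in the model, r is 0 and the error 5% in every row. That holds by construction, because age is the only omitted common cause in this model.

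The calculation uses one summary value per patient, not the planned mixed model of daily MQS. It shows direction and order of size only.

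**The case against.** The strongest reply is that nothing in the SAP is contradictory here. It predefines three sensible confounders, and frailty, nutrition, ASA, weight and SOFA are also collected without being listed. Function, severity and comorbidity are the main routes by which age would plausibly reduce mobilization, and all three are already adjusted for. If age has no effect beyond them, there is no bias, whatever its correlation with RFCSA. The SAP states no age–RFCSA or age–MQS association, and its description of sarcopenia does not mention age. Read as prediction conditional on the listed covariates, the hypothesis can be answered as planned.

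Much of this stands. A reader might infer that the planned analysis is demonstrably biased, or that a positive RFCSA result would simply be an age effect. The documents do not support either, because they supply none of the associations needed. A reader might also take 7–27% as the expected error. That range assumes a direct age effect of at least 0.15 SD per SD and scores only loosely related to age, and so leaves out the weak cases.

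The argument that the scores already contain age cannot be settled from the SAP. It mentions only "Admission laboratory data and vital signs to calculate the APACHE II score" and does not say whether the CCI is age-adjusted. Any age content would share a single coefficient with the other items of its score, so it need not remove the age effect completely. Nor does it help to read the confounder list as open-ended: the list is presented as predefined, and an open list would allow age to be added or dropped after the results are seen.

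**Conclusion.** The point holds as possible residual confounding. Age is collected, precedes the exposure, and is missing from both models behind the secondary aim's independence claim, with no stated reason. If age lowers muscle area and mobilization beyond what Barthel, APACHE2 and CCI capture, the bias runs towards a positive finding.

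Its size cannot be derived from the SAP. Under the stated assumptions the nominal 5% error ranges from no inflation, through about 5–13% with a weak direct effect or with scores that track age as closely as in the last row of the table, to about 27% in the worst corner of the grid. The grid is itself a choice, so 27% is not a bound. The primary outcome, its models and the sample size statement are unaffected.

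**What to change.** Add age, as a continuous variable, to the predefined confounders of both secondary-aim mixed models, and state that the sarcopenia yes/no model uses the same adjustment set. If the sponsor prefers the present list for the main model, a prespecified sensitivity analysis with age, or a stated reason why the three scores suffice, would be the minimum.

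The cost is one degree of freedom per model and no new data. Age may overlap with any age content in APACHE2 or CCI, which makes those coefficients harder to interpret but not the RFCSA coefficient. The RFCSA estimate loses some precision. At an age–RFCSA correlation of 0.5 in the base case, its standard error rises by a factor of √(0.937/0.75) = 1.12, before any gain from lower residual variance.

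### The secondary-aim models of daily MQS leave out PSS morbidity, ASA and enrollment GCS, which the SAP itself says influence mobilization dose, so the independent-predictor claim for RFCSA is open to confounding, mainly by procedural risk

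*SAP*

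**What the plan says.** The hypothesis in SAP Section 3 is worded as one of independence: "The primary hypothesis is that RFCSA is an independent predictor of mobilization dose in the SICU". The outcome is daily MQS: "The outcome for the secondary aim of the study is the repeatedly measured daily mobilization dose as quantified by the MQS". The analysis is a generalized linear mixed model, first with continuous RFCSA and then, as a secondary analysis, with sarcopenia yes/no. The adjustment set is given once: "Predefined confounders include the Barthel Index at hospital admission, APACHE2 and Charlson Comorbidity Index (CCI").

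Three other places in the SAP bear on that set:

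- **Section 2, Planned Sensitivity Analyses, Generalized propensity score.** "The propensity score will be generated from different covariates identified as influencing the exposure including APACHE, GCS at enrollment, ASA at admission, PSS-Morbidity". The list continues with variables that arise during the ICU stay. The exposure meant here is MQS, since the same paragraph says "we will categorize the mean mobilization dose (MQS) into two categories, high vs. low".
- **Section 2, Covariate Data and Primary analysis.** PSS morbidity is a predefined confounder of the MQS–ADD model, together with APACHE2 and sex-adjusted RFCSA.
- **Data collection, Baseline.** ASA is listed, as are "Glasgow Coma Scale motor component at enrollment, Absence of lower extremity (y/n), Pregnancy (y/n), Procedural Severity Score". Surgery before inclusion is recorded as yes or no.

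**The concern.** Mobilization dose is the exposure in the primary aim and the outcome in the secondary aim. A baseline variable that the SAP says influences mobilization dose is therefore, on the SAP's own account, a determinant of the secondary-aim outcome. Of the four baseline items on the propensity list, only APACHE is carried into Section 3.

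PSS morbidity is the clearest gap, because none of Barthel, APACHE2 or CCI measures surgical or procedural risk. If patients with higher procedural risk, higher ASA class or poorer motor response also tend to have smaller muscle area, part of their effect on mobilization would be credited to RFCSA. What is at stake is the word independent: RFCSA could be declared an independent predictor when it partly stands in for risk that the study has already recorded.

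**Working it through.** **1. The plan's own figure.** The only power statement concerns the primary outcome: correlation 0.25, 150 patients, alpha 0.05, power above 0.8. By Fisher's z, two-sided, power = Φ(√147 × atanh(0.25) − 1.96) = Φ(12.124 × 0.2554 − 1.96) = Φ(1.137) = 0.87. The statement holds, but says nothing about the secondary aim. The SAP gives no correlation of GCS, ASA or PSS with MQS or with RFCSA, so every effect size below is an assumption.

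**2. Covariates side by side.**

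| Variable | Said to influence MQS (propensity list) | Primary-aim model | Secondary-aim models | Baseline list |
|---|---|---|---|---|
| APACHE | yes | yes | yes | yes |
| PSS morbidity | yes | yes | no | as Procedural Severity Score |
| ASA | yes | no | no | yes |
| GCS at enrollment | yes | no | no | motor component only |

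The in-stay items on the propensity list (ventilation, sedation and delirium durations, opioids, vasopressors) are set aside. They arise after the RFCSA measurement or alongside the outcome, and do not belong in a baseline adjustment set.

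**3. Bias.** RFCSA and the omitted variables are patient-level, so I work with patient-mean MQS in n = 150. Treat the omitted variables as one risk index with standardized effect b on MQS and correlation ρ with RFCSA, both beyond the three covariates in the model. If RFCSA has no true effect, its expected standardized coefficient is b × ρ. With 150 − 3 − 3 = 144, the shift in the test statistic is d = bρ × √144 = 12bρ. The two-sided rejection rate is 1 − Φ(1.96 − d) + Φ(−1.96 − d).

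| b | ρ | bρ | d | Rejection rate |
|---|---|---|---|---|
| any | 0 | 0 | 0 | 0.05 |
| 0.2 | 0.2 | 0.04 | 0.48 | 0.08 |
| 0.2 | 0.3 | 0.06 | 0.72 | 0.11 |
| 0.3 | 0.2 | 0.06 | 0.72 | 0.11 |
| 0.3 | 0.3 | 0.09 | 1.08 | 0.19 |

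A simulation of patient-mean MQS, with 3 to 14 days per patient, b = 0.3 and ρ = 0.3, rejected in about 21% of trials with the index omitted and about 5% with it included.

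**4. Precision.** Let R²y and R²x be the share of remaining variance in MQS and in RFCSA that the three added covariates explain. The ratio of the RFCSA standard error after adding them to that before is √[(1 − R²y)/(1 − R²x)] × √(145/142), where 145 = 150 − 5 and 142 = 150 − 8 are the residual degrees of freedom.

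| R²y | R²x | SE ratio |
|---|---|---|
| 0.20 | 0 | 0.90 |
| 0.10 | 0 | 0.96 |
| 0.10 | 0.10 | 1.01 |
| 0.10 | 0.20 | 1.07 |
| 0 | 0.20 | 1.13 |

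The standard error falls only if the covariates explain more of MQS than of RFCSA. The largest precision gain needs R²x = 0, which is the case with no bias.

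**The case against.** The best case for the plan is that nothing here is a contradiction. The propensity list serves an exploratory analysis of MQS and ADD. Section 3 asks a different question and may use a different set, and a predictor of the outcome is not a confounder unless it is also related to the exposure. The SAP states no link between these variables and RFCSA. APACHE2 already carries acute physiology, CCI comorbidity and Barthel prior function. All of this stands. It limits the size of the problem and confines it mainly to procedural risk, plus whatever ASA and GCS add. It does not explain why PSS morbidity is a confounder in one aim and absent from the other, and it does not make the added adjustment harmful.

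The list might also be read as open-ended. Section 2 introduces the primary-aim confounders with the same verb and then treats them as a closed set. If the Section 3 list were open, the adjustment set would not be prespecified, although that section says its methods are.

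Two stronger readings are tempting. A reader might infer that the omission costs the RFCSA test power. The documents do not support this: the direction depends on two unknown quantities, and the standard error ratio runs from 0.90 to 1.13 over plausible values. A reader might also infer that physiological risk is left uncontrolled, but APACHE2 is in the model.

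**Conclusion.** The omission is established from the text: three baseline variables that the SAP says influence mobilization dose are on its collection list but absent from both secondary-aim models, without a reason. That leaves the independent-predictor claim open to confounding; it does not show that the claim would be wrong.

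The size is conditional. With 150 patients, an effect on MQS of 0.2 to 0.3 and a correlation with RFCSA of 0.2 to 0.3, a nominal 5% test would reject a true null in about 8% to 19% of trials. With zero correlation it stays at 5%. These inputs are assumptions, and overlap of ASA and GCS with APACHE2 and CCI would reduce the effect. The point rests on internal consistency and protection against bias, not on precision. It concerns a secondary, observational aim and is a moderate matter that costs little to settle.

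**What to change.** In Section 3, Statistical Analysis, extend the predefined covariates of both mixed models (continuous RFCSA and sarcopenia yes/no) from Barthel Index, APACHE2 and CCI to include PSS morbidity, ASA and the GCS motor component. Use admission or enrollment values only. Report the present three-covariate model alongside, so that a reader can see how far the RFCSA coefficient moves.

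Two details need wording:

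- PSS morbidity is a postoperative index and surgery is recorded as yes or no. Include a surgery indicator and set PSS to a fixed constant (for example 0) for non-surgical patients, so that they stay in the model. The indicator absorbs the arbitrary choice of constant.
- Confirm that the Procedural Severity Score on the baseline list is the PSS morbidity score of Section 2.

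This takes wording only: the variables are already on the baseline list. The price is three or four more patient-level terms in about 150 patients, some collinearity with APACHE2 and CCI, and possibly a wider interval or a smaller coefficient for RFCSA. If the three-covariate set is to remain the main model, the SAP should say why and prespecify the extended model as a sensitivity analysis.
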